#### 1. Case Administrative Information

Protocol/Study Number: \_\_\_\_\_

Study Design:  Interventional  Observational (If Observational:  Prospective  Retrospective)

#### 3. Subject Information

Subject ID # \_\_\_\_\_ Subject Gender:  Female  Male Subject DOB: mm  / dd  / yyyy

#### 4. Amgen Product Exposure

Amgen Product	Dose at time of conception	Frequency	Route	Start Date
				mm  / dd  / yyyy 

Was the Amgen product (or study drug) discontinued?  Yes  No

If yes, provide product (or study drug) stop date: mm  / dd  / yyyy

Did the subject withdraw from the study?  Yes  No

#### 5. Pregnancy Information

Pregnant female's LMP mm  / dd  / yyyy  Unknown

Estimated date of delivery mm  / dd  / yyyy  Unknown  N/A

If N/A, date of termination (actual or planned) mm  / dd  / yyyy

Has the pregnant female already delivered?  Yes  No  Unknown  N/A

If yes, provide date of delivery: mm  / dd  / yyyy

Was the infant healthy?  Yes  No  Unknown  N/A

If any Adverse Event was experienced by the infant, provide brief details:

\_\_\_\_\_

\_\_\_\_\_

Form Completed by:

Print Name: \_\_\_\_\_

Title: \_\_\_\_\_

Signature:

Date: \_\_\_\_\_

**AMGEN®** Lactation Notification Worksheet

Fax Completed Form to the Country-respective Safety Fax Line  
SELECT OR TYPE IN A FAX# US: [contact]

**1. Case Administrative Information**

Protocol/Study Number: \_\_\_\_\_

Study Design:  Interventional  Observational (If Observational:  Prospective  Retrospective)

**3. Subject Information**

Subject ID # \_\_\_\_\_ Subject Date of Birth: mm \_\_\_\_ / dd \_\_\_\_ / yyyy \_\_\_\_

**4. Amgen Product Exposure**

Amgen Product	Dose at time of breast feeding	Frequency	Route	Start Date
				mm ____ / dd ____ / yyyy ____

Was the Amgen product (or study drug) discontinued?  Yes  No

If yes, provide product (or study drug) stop date: mm \_\_\_\_ / dd \_\_\_\_ / yyyy \_\_\_\_

Did the subject withdraw from the study?  Yes  No

**5. Breast Feeding Information**

Did the mother breastfeed or provide the infant with pumped breast milk while actively taking an Amgen product?  Yes  No

If No, provide stop date: mm \_\_\_\_ / dd \_\_\_\_ / yyyy \_\_\_\_

Infant date of birth: mm \_\_\_\_ / dd \_\_\_\_ / yyyy \_\_\_\_

Infant gender:  Female  Male

Is the infant healthy?  Yes  No  Unknown  N/A

If any Adverse Event was experienced by the mother or the infant, provide brief details: \_\_\_\_\_

Form Completed by:

Print Name: \_\_\_\_\_ Title: \_\_\_\_\_

Signature: \_\_\_\_\_ Date: \_\_\_\_\_

**Appendix D. International Myeloma Working Group Uniform Response Criteria for Multiple Myeloma (IMWG-URC)**

Response	Subcategory a	Multiple Myeloma Response Criteria
	sCR b	

• CR as defined below and

• Normal SFLC ratio and

• Absence of clonal cells in bone marrowc by immunohistochemistry or immunofluorescencec

	CR b	

• Negative immunofixation on the serum and urine and

• Disappearance of any soft tissue plasmacytomas and

• < 5% plasma cells in bone marrowc

	VGPR b	

• Serum and urine M-protein detectable by immunofixation but not on electrophoresis or

• <math>\geq 90\%</math> reduction in serum M-protein with urine M-protein level <math>< 100</math> mg/24 hours

• If the serum and urine M-protein are not measurable, a decrease of <math>\geq 90\%</math> in the difference between the involved and unininvolved FLC levels required in place of the M-protein criteria. However, documentation of VGPR requires collection and analysis of 24 hour urine sample for UPEP and immunofixation and confirmed to be negative.

• If present at Baseline, a <math>\geq 50\%</math> reduction in the size of soft tissue plasmacytomas is also required.

	PR b	

• <math>\geq 50\%</math> reduction of serum M-protein and reduction in 24-hour urinary M-protein by <math>\geq 90\%</math> or to <math>< 200</math> mg/ 24 h

• If the serum and urine M-protein are unmeasurable, a <math>\geq 50\%</math> decrease in the difference between involved and unininvolved FLC levels is required in place of the M-protein criteria.

• If serum and urine M-protein are not measureable, and serum free light assay is also not measureable, <math>\geq 50\%</math> reduction in plasma cells is required in place of M-protein, provided baseline bone marrow cell percentage was <math>\geq 30\%</math>

• If present at Baseline, a <math>\geq 50\%</math> reduction in the size of soft tissue plasmacytomas is also required

Stable disease		

• Not meeting criteria for CR, VGPR, PR, or PD

Page 1 of 2

Footnotes defined on last page of this table

Response	Subcategory a	Multiple Myeloma Response Criteria
PD b		

• Any one or more of the following:

• Increase of <math>\geq 25\%</math> from lowest response value in:

○ Serum M-component and/or (the absolute increase must be <math>\geq 0.5</math> g/dL)

○ Urine M-component and/or (the absolute increase must be <math>\geq 200</math> mg/24 h)

○ Only in patients without measurable serum and urine M-protein levels; the difference between involved and uninvolved FLC levels. The absolute increase must be <math>>10</math> mg/dL

○ Bone marrow plasma cell percentages (absolute percentage must be <math>\geq 10\%</math>)

• Definite development of new bone lesions or soft tissue plasmacytomas or definite increase in the size of existing bone lesions or soft tissue plasmacytomase, f, g

• Development of hypercalcemia (corrected serum calcium <math>> 11.5</math> mg/dL or 2.65 mmol/L) that can be attributed solely to the plasma cell proliferative disorder

Page 2 of 2

Source: Durie 2006; Rajkumar 2011 (*modified for protocol purposes*).

CR = complete response; sCR = stringent complete response; FLC = serum light chain; MR = minor response; PD = progressive disease; PR = partial response; SFLC = serum free light chain; VGPR = very good partial response.

Note:

a Patients with measurable disease in both serum (SPEP) and urine (UPEP) at study entry are required to meet response criteria in both UPEP and SPEP in order to qualify for a MR or better. Conversely, it should be noted that criteria for PD only needs to be met, and confirmed, in one parameter. For patients without measurable protein on UPEP at Baseline, UPEP will need to be repeated to confirm a response.

b All response categories (CR, sCR, VGPR, PR) require 2 consecutive assessments made at any time before the institution of any new therapy, as well as no known evidence of progressive or new bone lesions if radiographic studies were performed. Radiographic studies are not required to satisfy these response requirements. Bone marrow, plasmacytoma, and skeletal survey assessments are not required to be confirmed by repeat testing. SD requires a duration of  $\geq 6$  weeks.

c Presence/absence of clonal cells is based upon the  $\kappa/\lambda$  ratio. An abnormal  $\kappa/\lambda$  ratio by immunohistochemistry and/or immunofluorescence requires a minimum of 100 plasma cells for analysis. An abnormal ratio reflecting presence of an abnormal clone is  $\kappa/\lambda$  of  $> 4:1$  or  $< 1:2$ .

d Determination of PD while on study requires 2 consecutive assessments made at any time before classification of PD and/or the institution of new therapy. Serum M-component increases of  $\geq 1$  g/dL from nadir are sufficient to define progression if starting M-component is  $\geq 5$  g/dL.

e Plasmacytomas: A definite increase in the size is defined as a  $\geq 50\%$  increase as measured serially by the sum of the products of the cross-diameters of the measurable lesion. A plasmacytoma is considered measurable if the longest diameter is at least 1 cm and the product of the cross diameters is at least 1 cm^2. Plasmacytomas of lesser size will be considered non-measurable.

f The requirement for bi-directional measurements applies only to plasmacytomas.

g The plasmacytoma specifications for PD are based on interpretation of the IMWG-URC and practical considerations for study execution.

Definition of Minimal Response per EBMT Criteria

Minimal Response	
Response Subcategory	Response Criteria
MR a	≥ 25 but < 49% reduction in serum M-protein and a 50–89% reduction in 24-hour urinary M-protein, which still exceeds 200 mg per 24 h
	If the serum and urine M-protein are not measurable, a decrease of 25%–49% in the difference between involved and uninvolved FLC levels is required in place of the M-protein criteria.
	For patients with nonsecretory myeloma only, 25–49% reduction in plasma cells in a bone marrow aspirate and on trephine biopsy, if biopsy is performed
	25–49% reduction in the size of soft tissue plasmacytomas (by radiography or clinical examination)

Sources: [Bladé 1998](#); [Kyle 2009](#).

EBMT = European Group for Blood and Marrow Transplantation; FLC = free light chain; MR = minimal response.

a The response category MR requires 2 consecutive assessments made at any time before the institution of any new therapy, as well as no known evidence of progressive or new bone lesions if radiographic studies were performed. Radiographic studies are not required to satisfy these response requirements. Bone marrow assessments are not required to be confirmed by repeat testing.

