### 7.1 Inclusion Criteria

- 101 Subject has provided informed consent prior to initiation of any study-specific activities/procedures
- 102 Age  $\geq$  18 years old at the time of signing the informed consent
- 103 Subject must have a pathologically documented, definitively diagnosed, multiple myeloma relapse, or refractory progressive disease after at least 2 lines of therapy for multiple myeloma (see [Appendix D](#) and [Appendix F](#) for further details). Prior therapeutic treatment or regimens must include a proteasome inhibitor and lenalidomide
- 104 Subject must be willing and able to undergo bone marrow aspirate per protocol (with or without bone marrow biopsy per institutional guidelines)
- 105 Measurable disease (assessed within 28 days prior to day 1), as indicated by one or more of the following:
  - Serum M-protein  $\geq$  0.5 g/dL
  - Urine M-protein  $\geq$  200 mg/24 hours
  - In subjects without detectable serum or urine M-protein: serum Free Light Chain (sFLC)  $\geq$  10 mg/dL ( $\geq$  100 mg/L) and an abnormal sFLC ratio
- 106 Eastern Cooperative Oncology Group (ECOG) performance status of  $\leq$  2
- 107 Hematological function, as follows, without transfusion support:
  - Absolute neutrophil count  $\geq$  1.0  $\times$  10^9/L
  - Platelet count  $\geq$  75  $\times$  10^9/L (in patients with  $<$  50% of bone marrow nucleated cells were plasma cells) or  $\geq$  50  $\times$  10^9/L (in patients with  $\geq$  50% of bone marrow nucleated cells were plasma cells) without transfusion or growth factor support

- Hemoglobin > 8 g/dL (> 80 g/L) Use of erythropoietic stimulating factors and red blood cell (RBC) transfusions per institutional guidelines is allowed, however most recent RBC transfusion must not be within 7 days prior to obtaining screening hemoglobin

108 Coagulation function as follows: PT/INR and PTT < 1.5 x Institutional Upper Limit of Normal (ULN)

109 Renal function as follows: estimated glomerular filtration rate based on Modification of Diet in Renal Disease calculation (MDRD) > 30 mL/min/1.73 m^2

110 Hepatic function, as follows: AST and ALT < 3 x ULN, Total bilirubin < 1.5 x ULN (except subjects with Gilbert's syndrome)

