##### **10.2.12.2 Immunofixation**

Immunofixation is done at screening and is required at next assessment only if SPEP or UPEP results are zero or undetectable.

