#### **10.2.12.4      Serum Free Light Chain**

Serum free light chain (sFLC) assay and ratio will be performed at each time point as specified in the Schedule of Assessments ([Table 6](#)).

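### Appendix D has no free-light-chain condition for CR, so a subject measurable only by sFLC who is immunofixation-negative and plasmacytoma-free from baseline can be scored CR without meeting PR or VGPR

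*Protocol*

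**What the plan says.** **Eligibility.** Protocol section 7.1, criterion 105, has a third route to measurable disease: "In subjects without detectable serum or urine M-protein: serum Free Light Chain (sFLC") of at least 10 mg/dL with an abnormal ratio. No minimum marrow plasma-cell percentage is set at entry.

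**CR.** Appendix D lists three conditions: "Negative immunofixation on the serum and urine"; "Disappearance of any soft tissue plasmacytomas"; and fewer than "5% plasma cells in bone marrow". None mentions FLC. The condition "Normal SFLC ratio" appears only in the sCR row, on top of CR.

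**Other categories.** The VGPR row has a substitute that begins "If the serum and urine M-protein are not measurable, a decrease of" and requires a 90% fall in the involved-minus-uninvolved FLC difference. PR requires a 50% fall and MR 25–49%. PD has an FLC rule for the same subjects.

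**Schedule.** Under section 10.2.12.4, "Serum free light chain (sFLC) assay and ratio will be performed at each time point" in the Schedule of Assessments. Under section 10.2.12.2, immunofixation after screening "is required at next assessment only if SPEP or UPEP results are zero or undetectable". Under section 10.2.12.3, marrow is repeated only to confirm CR.

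**Use.** SAP section 5 ranks CR above VGPR and PR in BOR and counts it in ORR. DOR runs from the first objective response. The SAP cites the IMWG criteria but gives no CR definition or FLC rule of its own.

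**The concern.** A response scale should be ordered, so that a subject in a higher category also meets the lower ones. For sFLC-only subjects this scale is not. VGPR, PR, MR and PD all follow the one measurable marker that is tested serially; CR does not.

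Two errors are possible. A subject whose FLC difference falls by less than 50% is not a PR, yet can enter ORR and DOR as a CR. A subject whose difference falls by 50% or more, but who does not reach VGPR, can be reported as CR instead of PR. Efficacy is one of the inputs to the dose and formulation recommendation, and the cohorts are small enough for one subject to be visible.

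**Working it through.** The plan states no figure to reproduce, so the check applies the Appendix D rows as a decision rule.

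**1. The rule.** Take an sFLC-only subject with negative immunofixation and no plasmacytoma from baseline, and an abnormal sFLC ratio throughout (so sCR is excluded). Vary the fall in FLC difference and the marrow result. Rises that would meet PD are left out.

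| Fall in FLC difference | Marrow 10% | Marrow 3% |
|---|---|---|
| 0%, 10% | SD | CR |
| 25%, 49% | MR | CR |
| 50%, 89% | PR | CR |
| 90%, 99% | VGPR | CR |

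At 10% marrow the scale is ordered by FLC. At 3% every subject is CR, including one with no fall. Example: the difference goes from 40 to 30 mg/dL, a fall of (40 − 30)/40 = 25%. That is half the fall needed for PR, and it is CR as written if the marrow shows 4%.

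**2. Do other provisions close the gap?**
- Appendix D requires two consecutive assessments for every response, but exempts marrow and plasmacytoma from repeat testing. Repeating a negative immunofixation that was negative at baseline adds nothing.
- An undetectable SPEP or UPEP triggers immunofixation. These subjects meet that trigger at entry.
- The marrow-based route to PR requires at least 30% plasma cells at baseline. The CR row has no baseline requirement, so a subject could enter already below 5%.
- The remaining Appendix D footnotes add no FLC condition for CR.

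**3. How many subjects?** Protocol section 5.5.5 reports responses in 28 IR and 8 GR subjects on OPomd, 36 in all. (The same paragraph also gives 23 OPomd subjects, but 36 + 9 on dexamethasone only = 45, its stated total, so 36 is used.) The sFLC-only share is not given. Assuming 5–20%: 0.05 × 36 = 1.8 and 0.20 × 36 = 7.2, or about 2 to 7. These are all sFLC-only subjects, not misclassified ones.

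**4. What is one subject worth?** GR: 1/8 = 12.5 points. IR: 1/28 = 3.6 points. If one reported responder in a group were such a case (exact 95% intervals):
- GR: 3/8 = 37.5% (8.5–75.5) would become 2/8 = 25.0% (3.2–65.1).
- IR: 20/28 = 71.4% (51.3–86.8) would become 19/28 = 67.9% (47.6–84.1).

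These are illustrations. The documents do not show that any such case occurred.

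**5. Which endpoint moves?** ORR changes only if the FLC fall is below 50%. At 50% or more the subject is already a responder, and only the BOR category can change.

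**6. With an FLC condition.** If CR also needs the 90% fall, the 3% marrow column becomes SD at 0–10%, MR at 25–49%, PR at 50–89%, and CR only from 90%. If a normal ratio is required as well, a subject at 90% or more with an abnormal ratio is VGPR.

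**The case against.** The strongest reply is that CR is far from automatic. It needs negative serum and urine immunofixation, no plasmacytoma, a marrow below 5%, two consecutive assessments, and no known new or progressive bone lesion. Criterion 105 names no assay for detectable M-protein, so some sFLC-only subjects may be immunofixation-positive at entry and must convert. Those with marrow at 5% or more must clear it, which is real evidence of response. A site would also have to suspect CR and take a marrow sample while sFLC was still high. All of this stands, and it narrows the affected group to subjects already immunofixation-negative and plasmacytoma-free, with marrow low at entry or patchily sampled. It does not restore the ordering for that group.

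A second reply is that the SAP names the revised IMWG criteria, while Appendix D is labelled as modified for the protocol, so the operative rule may lie elsewhere. But Appendix D is the only definition the documents contain, and the SAP states no rule that would override it.

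A third is that nothing formal depends on CR: all analyses are descriptive and the MTD rests on DLTs. That is correct and limits the consequence.

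A reader might infer that any sFLC-only subject can be called CR regardless of disease status, or that the reported response rates are inflated. The documents support neither. The other CR conditions still apply, and no misclassified subject is identified.

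**Conclusion.** The gap is real and follows from the text alone. For an sFLC-only subject who is immunofixation-negative and plasmacytoma-free from baseline, one marrow result below 5% decides CR, whatever the fall in FLC, and CR can be met without PR or VGPR.

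The number affected is unknown. Under the 5–20% assumption there are about 2 to 7 sFLC-only subjects among the 36, and only some of them could be misclassified. The effect is confined to secondary, descriptive endpoints, but one subject carries real weight in the GR group. The defect is worth correcting because the data needed are already scheduled. It does not call the dose-escalation result into question.

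**What to change.** Add to the CR row of Appendix D: *In subjects whose disease is measurable only by sFLC, CR also requires a normal sFLC ratio and must satisfy the VGPR FLC criterion.*

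Both parts are needed. The ratio is the condition sCR already uses, but PR and VGPR are defined on the difference. For example, involved and uninvolved levels of 10 and 5 mg/dL moving to 8 and 5 give a 40% fall in the difference (5 to 3) and a ratio of 1.6. Whether 1.6 is normal depends on a reference range that the documents do not give. Requiring the 90% fall keeps the categories ordered in any case, and sCR remains distinct through absence of clonal marrow cells.

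Put the same rule in SAP section 5, say there that Appendix D as amended governs the derivation, and apply it to BOR, ORR and DOR at the final analysis. Report how many subjects were sFLC-only, and list any whose category differs from the primary analysis.

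**Cost.** No new procedure is needed. The CR rate or ORR may fall slightly. Protocol section 5.5.5 already cites a Clinical Study Report (cutoff 02 December 2019, snapshot 21 August 2020), and both documents say the final analysis uses the primary-analysis methods. The change must therefore be declared as a departure from those methods, with a reconciliation against the reported results.

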## 6.2 Number of Sites

The study will be conducted at approximately 20 sites in the US and internationally. Sites that do not enroll subjects into an open cohort within 4 months of site initiation may be closed.

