#### **10.2.16 Clinical Laboratory Assessments**

Blood samples for clinical chemistry, hematology, and urine samples for urinalysis, will be collected at screening, and at time points specified in the Schedule of Assessments (Table 6). All tests (except for PK and [REDACTED]) are to be performed at a local laboratory and test results are to be recorded in the eCRF. Blood samples will be obtained by venipuncture before study drug administration. All laboratory tests must be reviewed by the investigator or qualified designee. Additional safety laboratory assessments may be performed if clinically indicated at the discretion of the investigator. The following tests listed in Table 8 will be conducted on samples collected by standard laboratory procedures.

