### **11.3 Reasons for Removal From Treatment or Study**

#### **11.3.1 Reasons for Removal From Treatment**

Reasons for removal from protocol-required investigational product(s) or procedural assessments include any of the following:

- subject request
- safety concern (eg, due to an adverse event)
- non-compliance (eg, procedural or dosing)
- requirement for alternative therapy
- pregnancy
- decision by Amgen (other than subject request, safety concern, or lost to follow-up)
- decision by investigator (other than subject request, safety concern, or lost to follow-up)
- death
- lost to follow-up
- confirmed disease progression per IMWG ([Appendix D](#))

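### The two calcium cut-offs printed for progression in Appendix D are not equivalent: 11.5 mg/dL is 2.87 mmol/L, not 2.65 mmol/L

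*Protocol*

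**What the plan says.** The PD row of Appendix D opens with "Any one or more of the following", so each listed criterion can define progression without the others. The last of them is hypercalcemia, with corrected serum calcium above 11.5 "mg/dL or 2.65 mmol/L) that can be attributed solely to the plasma cell proliferative disorder", so the hypercalcemia must also be due only to the plasma cell disorder. Footnote d to the same table adds a confirmation rule: "Determination of PD while on study requires 2 consecutive assessments made at any time before classification of PD and/or the institution of new therapy".

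Calcium is in the chemistry panel of protocol Table 8, with no unit given. Section 10.2.16 says that tests other than PK and a redacted item "are to be performed at a local laboratory and test results are to be recorded in the eCRF". Section 6.2 places the study at "approximately 20 sites in the US and internationally".

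PD is used in several places. It is an event for PFS (protocol 13.4.3.2; SAP Section 5), it ends a response for DOR, and it is the lowest category of best overall response (SAP Section 5). Section 11.3.1 lists "confirmed disease progression per IMWG" among the reasons for removal from treatment.

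**The concern.** A threshold printed in two units should be one threshold. Elsewhere the protocol's paired units do agree. In Section 7.1, hemoglobin is given as 8 g/dL and 80 g/L, and serum free light chain as 10 mg/dL and 100 mg/L. A site would reasonably take the calcium pair as equivalent too, and use whichever figure matches its laboratory report.

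If the figures differ, the same patient can be above the cut-off in one unit and below it in the other. With local laboratories and sites inside and outside the US, the cut-off applied could then depend on the reporting unit. At stake are the dates of some PFS and DOR events, the response category of some non-responders, and the point at which some subjects leave treatment.

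**Working it through.** **Inputs.** From Appendix D: 11.5 mg/dL and 2.65 mmol/L. From outside the documents: the molar mass of calcium, 40.078 g/mol. It is a physical constant and is treated here as an assumption, with a range shown below.

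**Formula.** mmol/L = (mg/dL × 10) / molar mass. In reverse, mg/dL = mmol/L × molar mass / 10.

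**Trying to reproduce the printed SI figure.** 11.5 × 10 / 40.078 = 115 / 40.078 = 2.869 mmol/L. The protocol prints 2.65, so the figure is not reproduced.

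**Reverse direction.** 2.65 × 40.078 / 10 = 10.62 mg/dL. The protocol prints 11.5.

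**Could rounding explain it?** No variant tried comes close:

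| Molar mass or factor | 11.5 mg/dL in mmol/L | 2.65 mmol/L in mg/dL |
|---|---|---|
| 40.0 (factor 0.25) | 2.875 | 10.60 |
| 40.078 | 2.869 | 10.62 |
| 40.08 | 2.869 | 10.62 |
| 40.1 | 2.868 | 10.63 |
| factor 0.2495 | 2.869 | 10.62 |

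The printed pair would agree only at a molar mass of 115 / 2.65 = 43.4 g/mol.

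**Size of the gap.** 2.869 − 2.65 = 0.219 mmol/L, which is 8.3% of 2.65 or 7.6% of 2.869. In conventional units, 11.5 − 10.62 = 0.88 mg/dL.

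**What the gap does.** A corrected calcium of 11.0 mg/dL is 110 / 40.078 = 2.74 mmol/L, which is above 2.65 mmol/L but below 11.5 mg/dL. The same holds for every value above 10.62 and up to 11.5 mg/dL.

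**Does either reading of *or* rescue the text?** If the values are meant as equivalents, the conversion is wrong. If meeting either one is enough, the lower value (2.65 mmol/L) always decides and 11.5 mg/dL has no function. The text is inconsistent on both readings.

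**Does another section settle it?** The footnotes to Appendix D do not mention calcium. SAP 9.5 says only that efficacy assessments follow the IMWG criteria. Neither document gives a unit convention, a conversion rule or an order of precedence.

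**The case against.** The strongest case on the other side accepts the arithmetic and disputes the consequence. Most of it stands.

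- **Calcium alone does not make PD.** The hypercalcemia must be attributed solely to the plasma cell disorder, and footnote d requires two consecutive assessments. Many subjects would also progress on M-protein, light chains, marrow, bone lesions or plasmacytomas. This narrows the exposure considerably. Confirmation does not remove the mismatch, because the second assessment is judged against the same cut-off as the first.
- **Mixed units are an inference.** No section says that any site reports calcium in mmol/L. Local laboratories and international sites make it plausible, no more. The contradiction in Appendix D exists without it.
- **The endpoints most exposed are secondary.** The primary endpoints are the MTD and treatment-related adverse events with laboratory changes, and neither uses PD. Overall response rate counts PR or better, so exchanging stable disease for PD leaves it unchanged. At most it could move if a subject were removed before a response developed. Best overall response is the best category reached, so a later PD does not cancel an earlier response.
- **Stopping treatment does not hang on this cut-off alone.** Section 6.1 also allows it for clinical progression as judged by the investigator.
- **The origin is unknown.** The table cites published criteria and says they were modified for this protocol. Those sources are not available here, so the pair may have been inherited. That does not make the two figures agree.

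A reader might go further and infer that the mismatch creates a false difference between doses or formulations. The documents do not support that: nothing shows that cohorts fill at sites with different units, and the analyses are described as hypothesis generating and mostly descriptive (protocol 13.4.1). A reader might also note that one misclassified subject moves a cohort of 4 to 10 by 25 to 10 percentage points. That is only 1/n on the safety-set sizes in protocol Table 2. It would be true of any single error and does not measure this one.

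**Conclusion.** Wrong as written; minor severity. The two printed cut-offs differ by 0.22 mmol/L (0.88 mg/dL), rounding does not explain the difference, and no other text resolves it. This rests only on the molar mass of calcium, and the conclusion is the same for every value from 40.0 to 40.1.

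The practical reach is narrow: subjects with corrected calcium above 10.62 and up to 11.5 mg/dL who satisfy the attribution and confirmation conditions and no other PD criterion. The documents do not allow that number to be estimated. It is probably small.

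A reader might conclude that PD is in fact declared at different calcium levels from site to site. That would need evidence that sites report in different units and apply the figure in their own unit, and the documents give neither. Which of the two thresholds was intended cannot be determined from the documents, and this review takes no position on it.

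**What to change.** The sponsor should reconcile the two values in Appendix D into one governing threshold, printed with its correct unit conversion. Because the criterion also feeds removal from treatment, the choice of value belongs to the sponsor's clinical team.

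That single threshold should then be applied uniformly to all sites whenever PD is assigned for PFS, DOR and best overall response. A sentence in the SAP definitions would make this explicit. Any PD already assigned on calcium should be rechecked against it.

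The cost is a one-line correction in Appendix D, an optional line in the SAP, and a review of the few records where calcium was the basis for PD. No new data are needed.
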